Connecting Women to Care: Home-based Psychotherapy for Women with MST Living in Rural Areas

NCT03429166

June 3, 2022 Data Plan and Analysis

Study Protocol Design Summary

1. Specific Aims

Military Sexual Trauma (MST) among women Veterans is a problem of epidemic proportion associated with significant mental health and functional impairment and substantial access to care barriers. Surveillance data indicate that one in four women Veterans reports MST when screened. Compared to women Veterans with other service-related stressors, those experiencing MST have greater mental health problems, are more likely to report difficulty in functioning in social, family and intimate relationships and are more likely to be unemployed and to report difficulties in finding a job. Nevertheless, women with MST engage less frequently in VA health care than other women Veterans. Barriers to care include distance from specialty services, financial difficulties, childcare and family responsibilities, and gender-related discomfort in male-dominated VA facilities. Research over the past decade has clearly identified the problems and concerns of women Veterans with MST but programs addressing their mental health needs and responsive to identified barriers are lacking. The current application addresses this gap.

[figure not shown]
The VA conceptualization of care as patient-centered includes a commitment to program development that is guided by the needs and preferences of specific populations. It is important to note that MST is an experience not a diagnosis, and therefore VA intervention responses to MST need to take into account women's preferences and perceptions of their problems as well as their diagnostic status. Among the most frequently reported problems identified by women with MST is a sense of social isolation and limited social support. From a diagnostic perspective, PTSD is among the most common and impairing of psychiatric disorder associated with MST. Over two decades of research has indicated that low social support and PTSD are reciprocally related such that low social support contributes to risk for and severity of PTSD and that PTSD decreases social support resources that are necessary for maintaining work, family and other social roles. This reciprocal reinforcement may be particularly true of women living in rural areas who experience substantial social isolation. Supported by the Office of Rural Health, we evaluated a remotely delivered, evidence-based social skills intervention, Skills Training in Affective and Interpersonal Regulation (STAIR) which simultaneously addresses social concerns and PTSD symptoms to rural women Veterans with MST at their local VA clinic. Several studies in community samples have demonstrated the effectiveness of STAIR. Findings for the women Veterans were similar: significant improvements in PTSD symptoms, perceived social support and social engagement were observed, along with very high satisfaction with the program.

Given these findings, the current study proposes to conduct a Hybrid Type 1 effectiveness-implementation design to assess the effectiveness of STAIR relative to a nonspecific active comparator, Present Centered Therapy (PCT) among women Veterans with MST, with dedicated resources to ensure engagement of those living in rural areas. We will evaluate remote delivery of the treatment to the home rather than a VA clinic. Recent research indicates that women Veterans prefer home-based video teleconferencing (HBVT) compared to clinic-based video teleconferencing (CBVT). In-home delivery may be of perceived value to women Veterans as it is responsive to the particular challenges of childcare and family responsibilities and the gender-related discomfort that can be experienced at a VA facility.

This proposal brings together the evaluation of a treatment as well as a delivery strategy each of which has strong face validity and supporting evidence indicating their relevance to women Veterans with MST, particularly those living in rural areas. If successful, the program will decrease social concerns and PTSD symptoms and increase use of mental health care in a highly burdened and underserved

Veteran population. The study has two aims:

- 1. To evaluate the effectiveness of HBVT-delivered STAIR compared to HBVT-delivered PCT via a randomized controlled trial. It is hypothesized that STAIR will be superior to PCT in reducing PTSD and related symptoms and in improving perceived social support, community engagement and social functioning. Assessments will occur five times: baseline (week 0), mid-treatment (week 5), post-treatment (week 10), 2 month follow-up (week 18) and 4 month follow-up (week 26).
- 2. To employ a multi-stakeholder mixed-methods evaluation of the delivery of STAIR via HBVT, based on two integrated frameworks: the Consolidated Framework for Implementation Research (CFIR) and the Replicating Effective Programs (REP). The evaluation will (a) elucidate facilitators and barriers of implementing STAIR via HBVT and (b) contextualize the quantitative findings of the clinical trial to enhance our understanding of both treatment processes and effectiveness.

2. Data Analysis for Effectiveness Trial

Preliminary analyses will include screening for normality, missingness, and equivalence of random assignment. Independent samples t-tests and chi-square tests of independence will be conducted to determine the presence of any significant baseline differences between key characteristics of individuals assigned to STAIR versus PCT. Baseline characteristics that differed by treatment condition or are associated with missingness will be used as covariates in the primary analyses. Analyses will be performed according to the intention-to-treat principle using the final sample derived from eligible participants.

To examine whether treatment condition predicted change in outcome variables, piecewise mixed-effects regression models will be estimated in R using package Ime4. One slope estimates change during the treatment period, and a second slope estimates change from posttreatment through 4-month follow-up in order to assess maintenance of treatment gains. A COVID-19 pandemic status covariate will be created by cross-referencing the date of each assessment with the date that the state of emergency was declared (03/04/2020). Interactions between time and treatment condition will be the main parameters of interest to test our hypotheses.

Primary Hypotheses

Hypothesis 1.1. STAIR will be superior to PCT regarding improvement in PTSD at post-treatment and through 2 and 4 month follow-up as measured by the CAPS-5 and PCL-5.

Hypothesis 1.2. STAIR will be superior to PCT regarding improvement perceived social support at post-treatment and through 2 and4 month follow-up as measured by the ISEL.

Hypothesis 1.3. STAIR will be superior to PCT regarding improvement in social functioning as measured by increased social/community engagement and increased weekly social activities measured, respectively, by the WHODAS 2.0 and the SAM.

Hypothesis 1.4 STAIR will be superior to PCT regarding improvement in trauma-related symptoms including emotion regulation problems (DERS), depression (BDI) and posttraumatic maladaptive beliefs (PMBS).

3. Data Analysis for the Qualitative Investigation

Evaluation. We will conduct formative evaluations via the interview with three key stakeholder groups; administrative staff (n = 4), clinicians (n=5) and patients (n=30) across both sites. Aadministrative staff at each site including the project coordinators and TMH clinic leaders will be interviewed at the end of the study. The 5 cclinicians will be interviewed twice. the first time at the halfway point of the patient enrollment period, and again at the end of the trial after they complete their final case. This will allow us to identify challenges that might impede initiation of implementation and will also allow us to examine whether clinician perspectives shift after they gain additional experience with the technology and with the intervention. Lastly, we will interview a random sample of patients (n=30, 15 from each site) throughout the course of the study, at the end of their treatment experience to assess facilitators and barriers as related to the perceived benefit of the therapy, the experience of obtaining their treatment at home and the challenges and benefits of using the technology. We considered integrating a separate framework to guide patient interviews since patient-related constructs are underrepresented in many implementation frameworks including CFIR, but determined that CFIR constructs are relevant to, and can be adapted to apply to patients, and did so to facilitate the interpretation of the data. We will also collect quantitative data, using measures that have been identified as predictors of effective implementation or reflect constructs relevant to effective implementation. These include the clinician Perceived Characteristics of Intervention Scale (PCIS) and for the patient, the Clinical Satisfaction Questionnaire (CSQ-8) and the Working Alliance Inventory (WAI). The WAI will be helpful in assessing the strength of the therapeutic alliance under conditions of remote delivery of treatment (relevant to relative advantage, patient preferences, and clinician attitudes and self-efficacy).

Contextualizing Quantitative Data. The mixed methods evaluation data will be used to help contextualize the quantitative findings of the clinical trial to enhance our understanding of both treatment processes and effectiveness. For example, we might discover that clinicians who struggle to maintain fidelity (quantitative data) have lower scores on the Perceived Characteristics of Intervention Scale (PCIS) (quantitative), and are more likely to perceive STAIR as less compatible with veterans' needs (qualitative). Such a finding would have implications for selection of appropriate implementation strategies. We can also enhance our understanding of patient data. For example, we might wish to learn whether veterans who score

Page 4 CWC

more highly on avoidance have different perspectives on receiving STAIR by telehealth to determine whether adaptations need to be made to the intervention or delivery format, or if specific implementation strategies may be needed to enhance engagement for veterans of this nature in future implementation efforts.

Analyses: We will conduct formative evaluations via the interview with three key stakeholder groups; administrative staff (n = 4), clinicians (n=5) and patients (n=30) across both sites. Administrative staff at each site including the project coordinators and TMH clinic leaders will be interviewed at the end of the study. The 5 cclinicians will be interviewed twice, the first time at the halfway point of the patient enrollment period, and again at the end of the trial after they complete their final case. This will allow us to identify challenges that might impede initiation of implementation and will also allow us to examine whether clinician perspectives shift after they gain additional experience with the technology and with the intervention. Lastly, we will interview a random sample of patients (n=30, 15 from each site) throughout the course of the study, at the end of their treatment experience to assess facilitators and barriers as related to the perceived benefit of the therapy, the experience of obtaining their treatment at home and the challenges and benefits of using the technology. We considered integrating a separate framework to guide patient interviews since patient-related constructs are underrepresented in many implementation frameworks including CFIR, but determined that CFIR constructs are relevant to, and can be adapted to apply to patients, and did so to facilitate the interpretation of the data. We will also collect quantitative data, using measures that have been identified as predictors of effective implementation or reflect constructs relevant to effective implementation. These include the clinician Perceived Characteristics of Intervention Scale (PCIS) and for the patient, the Clinical Satisfaction Questionnaire (CSQ-8) and the Working Alliance Inventory (WAI). The WAI will be helpful in assessing the strength of the therapeutic alliance under conditions of remote delivery of treatment (relevant to relative advantage, patient preferences, and clinician attitudes and self-efficacy).

Contextualizing Quantitative Data. The mixed methods evaluation data will be used to help contextualize the quantitative findings of the clinical trial to enhance our understanding of both treatment processes and effectiveness. For example, we might discover that clinicians who struggle to maintain fidelity (quantitative data) have lower scores on the Perceived Characteristics of Intervention Scale (PCIS) (quantitative) and are more likely to perceive STAIR as less compatible with veterans' needs (qualitative). Such a finding would have implications for the selection of appropriate implementation strategies. We can also enhance our understanding of patient data. For example, we might wish to learn whether veterans who score more highly on avoidance have different perspectives on receiving STAIR by telehealth to determine whether adaptations need to be made to the intervention or delivery format, or if specific implementation strategies may be needed to enhance engagement for veterans of this nature in future implementation efforts.

Page 5 CWC

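### Covariates for the primary models are picked by between-arm baseline tests instead of being fixed in advance, and the plan does not say how they would act on the tested slopes

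*Combined protocol and SAP*

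**What the plan says.** Section 2 (Data Analysis for Effectiveness Trial) opens with screening: "Preliminary analyses will include screening for normality, missingness, and equivalence of random assignment". Independent-samples t-tests and "chi-square tests of independence will be conducted to determine the presence of any significant baseline differences between key characteristics" of the two arms follow. The selection rule is then: "Baseline characteristics that differed by treatment condition or are associated with missingness will be used as covariates in the primary analyses".

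The same section describes the model as a piecewise mixed-effects regression: "One slope estimates change during the treatment period, and a second slope estimates change from posttreatment through 4-month follow-up". It names the tested quantities: "Interactions between time and treatment condition will be the main parameters of interest to test our hypotheses". The only covariate fixed in advance varies over time: "A COVID-19 pandemic status covariate will be created by cross-referencing the date of each assessment".

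The documents do not list the key characteristics to be tested. They give no threshold for a difference or for an association with missingness, and no form of entry for the selected covariates. They do not say whether the two arms have separate or common baseline means in the model.

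**The concern.** The rule has two limbs. The limb based on association with missingness has a rationale of its own under a missing-at-random assumption; there the problem is only that its candidates, threshold and form of entry are unstated. The between-arm limb is unsound as a selection method. Allocation is random, so the test picks up chance imbalance, whether or not the variable predicts change in the outcome.

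Three things are at stake:

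- The primary model cannot be written down before the arms are compared.
- A variable that predicts change is adjusted for only when chance makes it imbalanced, so the precision of a fixed list is forgone in the other trials.
- The hypotheses are tested on slopes, while a time-fixed covariate entered as a main effect acts on level. A report could then say that an imbalance was adjusted for when the tested parameter had hardly moved.

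**Working it through.** **Inputs from the documents.** Two randomised arms; assessments at weeks 0, 5, 10, 18 and 26 (section 1); two slopes and their interactions with treatment (section 2); eight outcome scales named in the hypotheses (CAPS-5, PCL-5, ISEL, WHODAS 2.0, SAM, DERS, BDI, PMBS). The plan gives no figure to reproduce: no sample size, significance level, variance or dropout rate is stated. Everything below that needs one is an assumption.

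**1. Chance selection.** With k independent tests at 0.05, P(at least one selected) = 1 − 0.95^k.

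- k = 8 (one per named scale): 1 − 0.663 = 0.337
- k = 10: 1 − 0.599 = 0.401
- k = 20: 1 − 0.358 = 0.642

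With eight tests correlated at 0.3 or 0.5, the figure is 30% or 25%.

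If exactly one of the k candidates predicts the slope, the chance that it is among those selected, given that something is selected, is 0.05 / (1 − 0.95^k) = 0.149, 0.125 and 0.078. Most selections therefore fall on variables that do not matter.

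**2. What a main effect does to the slopes.** With complete data and no time-varying covariate, each participant's five scores reduce to an intercept and two slopes. Let x be the selected covariate.

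- *Separate baseline means, x as main effect.* The intercept is regressed on arm and x, and each slope on arm only. The slope regressors are a subset of the intercept regressors, so generalised least squares (GLS) gives the plain difference in mean slopes. Dropping x leaves it the same.
- *Common baseline mean, x as main effect.* The intercept is regressed on x without arm. The subset property fails, the slope estimate borrows from the observed intercept difference, and x alters it.
- *x crossed with both slopes.* With separate baseline means, the slope difference becomes the raw difference minus (coefficient of x on slope) × (difference in mean x).

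One simulated complete dataset, fitted with estimated variances, shows the first and third cases. The treatment-period slope difference was 0.2412 (SE 0.1416) both without x and with its main effect. It was 0.1179 (SE 0.1386) with x crossed: a move of (0.2412 − 0.1179) / 0.1416 = 0.87 SE.

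**3. Size of the shift.** Known-variance GLS, no treatment effect.

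- Setting A: 80 per arm; variances 0.6 (intercept), 0.6 (first slope), 0.1 (second slope), 0.4 (residual); only trials in which the slope predictor was significantly imbalanced.
- Setting B: 50, 75 or 100 per arm; covariate effect 0.5 on level and 0.3 on the first slope; all trials.

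| Entry and conditions | Mean shift of treatment-period slope |
|---|---|
| Main effect, separate baselines, complete data (A and B) | 0.000 SE |
| Same, with COVID-19 term (A) | 0.005 to 0.006 SE, maximum 0.08 |
| Same, no COVID-19 term, 29% random dropout (A) | about 0.05 SE |
| Same, 30% dropout unrelated to x (B) | 0.05 to 0.07 SE, maximum 0.30 |
| Same, 30% dropout driven by x in opposite directions by arm (B) | 0.06 to 0.17 SE, maximum 0.51 |
| Main effect, common baseline mean, complete data (A, two runs) | 0.245 and 0.32 SE, against the imbalance |
| Crossed with both slopes, separate baselines (A) | 0.45 to 0.99 SE as x explains 10% to 40% of slope variance |

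In the arm-differential dropout case the main effect removed only about 10% to 33% of the resulting bias (for example −0.085 to −0.058: 0.027 / 0.085 = 32%). Crossed terms brought it to about zero.

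Under a common baseline mean, crossing moved the estimate by 1.01 SE in the run that gave 0.245. Against that, main-effect entry achieves 0.245 / 1.01 = 0.24 and 0.32 / 1.01 = 0.32: about a quarter to a third.

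**4. Error rates and power (Setting A).**

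- Overall type I error was 4.9% to 5.2% with main effects and 4.3% to 5.0% with crossed terms.
- In trials where the slope predictor itself was imbalanced (25% of slope variance explained, complete data, separate baselines), rejection under the null was 10.7% with no covariate, 10.7% with its main effect and 5.3% with crossed terms.
- When any of 8 to 20 candidates triggers the rule and one of them predicts the slope, null rejection under main-effect entry is 5.0% to 6.4%.
- With crossed entry, test-based selection gave up 0, 1 to 2, 3 to 6 and 4 to 10 points of power against a fixed three-covariate list, when one covariate explained 0%, 10%, 25% or 40% of slope variance.

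**The case against.** The strongest reply is that little harm follows. Type I error is preserved overall, and a chance imbalance is no worse than in an unadjusted analysis. The power forgone is zero if no covariate predicts change, and no document shows that one does. The plan does not say that covariates enter as main effects, so the slope problem may never arise. The sample sizes, variances and dropout rates are all assumed. Crossing covariates with the slopes is one modelling choice among several. All of this stands, and it limits the point to a cheap improvement in prespecification and method.

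A reader might infer more: that the plan leaves the tested slopes exactly, or essentially, unadjusted. The documents do not support that. The result needs main-effect entry and separate baseline means by arm, and neither is stated. Separate means are the usual form, but under a common mean the main effect gives a partial correction. In the two runs above, null rejection among imbalanced trials fell from 13.3% to 9.3% (300 runs) and from 12.5% to 8.0%. Nor is the shift under dropout always slight: the rule also selects covariates linked to missingness, and arm-differential dropout moved the estimate by up to about 0.5 SE in an extreme assumed case. A reader might also infer an inflated false-positive rate; the overall rates above show none.

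The reply does not rescue the between-arm tests. They are a stated rule, and nothing elsewhere in the documents supplies a list, a threshold or a form of entry.

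**Conclusion.** The point holds as a should-fix matter. Selecting primary-model covariates by between-arm tests rests on chance differences, does not target predictors of change, and leaves the primary model undefined until the arms are compared. This follows from the text of section 2 and needs no assumption beyond randomisation. The 34%, 40% and 64% selection probabilities assume independent tests at 0.05.

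The effect on the tested slopes is conditional. With main-effect entry and separate baseline means it is nil for complete data without a time-varying covariate, and small when dropout is unrelated to the covariate. With a common baseline mean, or with dropout that depends on the covariate and differs by arm, the correction is partial. The practical harm is a claim of adjustment that may not apply to the tested parameter, plus precision forgone if some covariate predicts change. Confidence is high in the reading of the plan and lower in the sizes.

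**What to change.** - Delete covariate selection by between-arm tests and report the baseline table descriptively.
- Before arm-level outcomes are seen, fix one short covariate list for all models: site (section 3 refers to "clinicians (n=5) and patients (n=30) across both sites") plus a few already collected baseline variables that the sponsor expects to predict change. Leave out an outcome's own week-0 score wherever week 0 is a response in that model; section 1 counts it among the five assessments.
- State whether baseline means are free or constrained by arm, and enter covariates in a form that acts on change, for example with interactions with both slopes.
- Keep predictors of missingness, chosen from a named candidate list by one prespecified rule and threshold on data pooled over arms, and entered in the same form. This step remains data-driven but does not use arm.
- If arm-level outcomes have already been seen, disclose the covariates that the rule selected and report the fixed-covariate analysis alongside.

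The cost is SAP wording and, with slope interactions, two extra terms per covariate compared with main-effect entry. The downside is a few degrees of freedom and about 0.3 points of power per covariate that does not predict change at an assumed 80 per arm (0.6 at 50, 0.2 at 120).

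### The Aim 1 model names no site term although patients come from two sites; if symptom course differs by site, a little precision is lost

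*Combined protocol and SAP*

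**What the plan says.** The two sites appear only in section 3 (Data Analysis for the Qualitative Investigation). Both its Evaluation and its Analyses paragraphs plan to interview "a random sample of patients (n=30, 15 from each site" and to interview administrative staff at each site.

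Section 2 (Data Analysis for Effectiveness Trial) describes the Aim 1 model: "piecewise mixed-effects regression models will be estimated in R using package Ime4". Its time structure is: "One slope estimates change during the treatment period, and a second slope estimates change from posttreatment through 4-month follow-up". The tested quantities are stated as follows: "Interactions between time and treatment condition will be the main parameters of interest to test our hypotheses". One covariate is named in advance: "A COVID-19 pandemic status covariate will be created by cross-referencing the date of each assessment".

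Other covariates depend on the data. Tests look for "any significant baseline differences between key characteristics of individuals assigned to STAIR versus PCT", and then: "Baseline characteristics that differed by treatment condition or are associated with missingness will be used as covariates in the primary analyses". The key characteristics are not listed. Site is not named as a fixed effect, a random effect, an interaction with time or a stratification factor. The allocation method is not described.

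**The concern.** Site is known for every woman before treatment starts and can be fitted in any model. If women at the two sites improve at different rates, a model without site by time counts that difference as unexplained variation between women. The standard errors of the time-by-treatment terms, on which Hypotheses 1.1 to 1.4 rest, are then somewhat larger than they need to be.

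The covariate rule does not settle this. Whether site enters depends on the observed data, so it could enter after one set of results and not after another. Even then, nothing says that it would be interacted with the slopes. A site main effect shifts the level at every visit and leaves the slope comparison alone. At stake are some precision and one analysis choice left open.

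**Working it through.** The document gives no sample size, SD, site split, alpha or power, so there is no stated figure to reproduce. Every size below rests on assumed values.

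**1. Precision.** Let d be the site difference in change, in SDs of change, with half the women at each site. A two-level factor with an equal split explains d²/4 of the variance, so the standard error with site in the model is √(1 − d²/4) of the one without.

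| d (assumed) | d²/4 | √(1 − d²/4) | SE smaller by |
|---|---|---|---|
| 0.2 | 0.0100 | 0.995 | 0.5% |
| 0.3 | 0.0225 | 0.989 | 1.1% |
| 0.5 | 0.0625 | 0.968 | 3.2% |

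**2. Power.** Now let g be the difference in within-site SDs. Omitting site multiplies the variance by 1 + g²/4: 1.010, 1.031 and 1.063 for g = 0.2, 0.35 and 0.5. Take two-sided alpha 0.05, 1:1 allocation not stratified by site, and an effect that gives 80% power with site adjusted. Power without site is then 79.6%, 78.8% and 77.6%, a loss of 0.4 to 2.4 points.

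**3. Chance imbalance, if allocation was not stratified by site.** The between-arm difference in site share has SD √(4 × 0.25/N): 0.10 at an assumed total N of 100 and 0.071 at 200. Multiplied by g, this gives noise of 0.02 to 0.05 SD at N = 100 (treatment SE √(4/100) = 0.20) and 0.014 to 0.035 SD at N = 200 (SE 0.141). This is the same loss as in step 2 and is not added to it. At N = 100 and g = 0.5, 0.20² + 0.05² = 0.0425, which is 0.04 × 1.0625. The unadjusted standard error already carries this noise, so the test is valid.

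**4. If allocation was stratified by site.** The imbalance is largely controlled, but the reported standard error is too large. The true alpha of a nominal 0.05 test is about 0.049, 0.047 and 0.043 for g = 0.2, 0.35 and 0.5.

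**5. Would the covariate rule catch it?** At an assumed 5% chi-square screen and an equal site split, imbalances up to 1.96 × 0.10 = 0.196 (N = 100) or 1.96 × 0.071 = 0.139 (N = 200) pass unflagged. A 10-point imbalance moves the treatment difference by 0.02 to 0.05 SD for g = 0.2 to 0.5.

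**6. Main effect or interaction?** A small simulation used 60 data sets, 160 women, the five planned visits, complete data and a site gap of 0.5 outcome units in the treatment-period slope. A site main effect left the time-by-treatment estimate unchanged (mean absolute change about 6 × 10⁻¹⁵). Adding site by both slopes moved it by 0.033 on average and lowered the mean model SE from 0.159 to 0.155. The empirical SD went from 0.1535 to 0.1527; 60 runs are too few to measure that gain.

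**The case against.** The strongest objection is that the point is immaterial. The gain is about 1% or less unless the sites differ by more than roughly 0.3 SD in change, and nothing in the document shows that they differ at all. Treatment is delivered by video to the home, which may weaken any site influence on symptom course. This stands, and it keeps the point minor.

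It can also be said that the covariate rule does not exclude site, and that a chi-square test suits a two-level factor. That is true, but entry would depend on the data, and a main effect would not act on the tested slopes.

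Four stronger readings are tempting and are not supported:

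- **Bias or an invalid test.** Treatment is randomised, so omitting site causes no systematic bias, and the test is valid or slightly conservative.
- **Both harms at once.** Noise from chance imbalance and over-wide standard errors belong to different allocation schemes, and the document describes neither.
- **The plan itself treats site as prognostic.** The 15 and 15 split is a sampling choice for interviews. Administrative staff at each site are documented; differing referral populations are not.
- **Aim 2 requires treatment effects by site.** Aim 2 does not mention site-specific barriers, and the examples of contextualising concern clinician fidelity and patient avoidance.

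**Conclusion.** The point holds as a minor, conditional gap in specification. The plan has two sites, no pre-specified site term, and a covariate rule that neither guarantees site nor ties it to the slopes. If symptom course differs between sites by an assumed 0.2 to 0.5 SD, with an equal split, standard errors are larger than necessary by an amount that adjustment would cut by about 0.5% to 3.2%. If the sites follow the same course, there is essentially no loss. No conclusion of the trial is put in doubt by this alone. The sizes depend on the assumed site difference and split, and the power and imbalance figures also on the assumed alpha, allocation and N.

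**What to change.** Add to the model description in section 2:

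> Site (two levels) will enter every Aim 1 model as a fixed effect, with its interactions with both time slopes, whether or not it differs by arm.

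A fixed effect is appropriate because two levels are too few for a random site effect. State also whether randomisation was stratified by site.

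The cost is one sentence and three fixed-effect parameters per model (site, and site by each slope), with no new data. If outcomes have already been analysed by arm, label the adjusted model as added afterwards.

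A STAIR minus PCT contrast by site is optional and should be descriptive only. The three parameters cannot supply it, because that model imposes one common contrast. It would need further site-by-treatment-by-slope terms or separate fits. At an equal split each site has half the women, so each contrast has a standard error of about √2 = 1.4 times the pooled one.
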